4.3. Justification for Dose

A single oral dose of 100 mg PF-06865571 will be used in this study. Dosing will occur in the fed state, consistent with previous clinical studies with PF-06865571. This dose has been selected based on prior experience in healthy participants and also takes into considerations that participants with varying degrees of hepatic impairment may have an increase in plasma PF-06865571 exposure. PF-06865571 was found to be well-tolerated with single doses up to 1500 mg (C2541001) and repeated doses up to 1800 mg/day (600 mg Q8H; C2541002) with the maximum tolerated dose not identified when administered to healthy adult participants. The PK of PF-06865571 is approximately dose-proportional, and the results at the proposed dose of 100 mg in this study can be extrapolated to other doses. While the PF-06865571 dose in this study represents half the maximum total daily dose/exposure of 300 mg BID envisioned in the Phase 2b, dose-ranging/dose-finding study, it is likely to be within the efficacious dose range (based on effect on liver fat observed following 14-days of dosing in those with NAFLD in Study C2541005).

For a single 100 mg dose of PF-06865571, Simcyp[®] simulations predict C_{max} increases of 1.2-, 1.3-, and 1.5-fold in participants with Child-Pugh classifications A, B, and C, respectively. AUC_{inf} increases of 1.4-, 2.1-, and 2.9-fold, respectively, are also predicted. The terminal $t_{1/2}$ is predicted to increase by <2-fold. In addition, these predictions are in line with less than 3-fold exposure increases observed in participants with moderate or severe hepatic impairment in clinical studies with sensitive CYP3A substrates, including midazolam and triazolam.^{4,5} Thus, a 3-fold increase likely represents the worst-case estimate for change in plasma exposure in this study in those with severe hepatic impairment and are not likely to pose a safety concern if observed in this study.

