2.3. Benefit/Risk Assessment

PF-06865571 is not expected to provide any clinical benefit to participants in this study. This study is designed primarily to generate pharmacokinetic data to inform further clinical development in the target population of patients with NASH. The data from this study will contribute to dosing recommendations of PF-06865571 for the treatment of NASH acknowledging that the target patient population includes those with varying degrees of hepatic impairment.

PF-06865571 has been administered as single doses in healthy subjects, as repeated doses in healthy adults and patients with NAFLD, and as modified-release formulation, as well as in combination with metformin. It has been observed to be well-tolerated with an acceptable safety profile at single oral doses as high as 1500 mg and repeated, oral doses of up to 1800 mg/day (as 600 mg every 8 hours [Q8H]) for a duration of up to 14 days with the maximum tolerated dose not identified. As of the issuance of this protocol, no specific human risks have been identified. The clinical impact of any *potential* risks in this study will be minimized through the proposed close, inpatient monitoring during the dosing period along with the selection of a dose (100 mg) which is 15-fold lower than the highest single dose administered thus far.

Based on the safety profile of PF-06865571 observed in clinical studies to date, the risk to the participants in this study is deemed to be minimal. More detailed information about the known and expected benefits and risks and reasonably expected adverse events of PF-06865571 may be found in the investigator’s brochure for PF-06865571, which is the single reference safety document (SRSD) for this study.

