4.2. Scientific Rationale for Study Design

This study involves participants with varying degrees of hepatic impairment and participants without hepatic impairment, matched for age as well as body weight (and gender as much as practically possible). A single dose of PF-06865571 is proposed since single dose plasma PK is generally predictive of exposure upon repeated dosing, especially given that the observed relatively short terminal half-life ($t_{1/2}$) of PF-06865571 resulted in minimal accumulation upon repeated dosing of both Q8H and Q12H frequency.

CCI [REDACTED]

[REDACTED] serial PK samples will be collected over 48 hours in participants without hepatic impairment (Cohort 1). CCI [REDACTED]

[REDACTED] serial PK samples will be collected over 72 hours postdose to adequately characterize the elimination phase of the plasma concentration-time profile in the cohorts with varying degrees of hepatic function (Cohorts 2-4).

Malnutrition is prevalent in patients with chronic liver disease, and regular meals are an important aspect for their health. CCI [REDACTED]

[REDACTED] PF-06865571 administration is planned to occur with the morning standard meal in this study to ensure consistency with the intended dosing scheme in the target patient population.

In general, participants with normal hepatic function (Cohort 1) will abstain from all concomitant treatments, except for the treatment of adverse events. Participants with impaired hepatic function (Cohorts 2, 3, and 4) are permitted to be on stable doses of background medications for the management of their concomitant medical condition(s) with some exclusions. Specifically, strong CYP3A inhibitors, strong and moderate CYP3A inducers, and time-dependent inhibitors of CYP3A are excluded from this study in participants with impaired hepatic function ^{CCI}

^{CCI} In addition, moderate CYP3A inhibitors will not be co-administered with PF-06865571 on Day 1 of this study. Similarly, BCRP substrates (eg, rosuvastatin) and sensitive CYP2C9 substrates will not be administered on Day 1 ^{CCI}

^{CCI} P-gp inhibitors (eg, digoxin) are excluded from this study. ^{CCI}

^{CCI} Participants taking metformin must not take a morning dose of metformin on Day 1 of this study.

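### Does the wrong dose fraction in Protocol 4.3 (100 mg described as half of 300 mg BID) call for a change to the plan?

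*Protocol*

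**What the plan says.** The study dose is stated plainly in Protocol 4.3: "A single oral dose of 100 mg PF-06865571 will be used in this study". The same figure appears in Protocol 2.1, 4.1 and 6.1 and in SAP Sections 2 and 2.1. Section 4.3 then adds, as a concession, that this dose "represents half the maximum total daily dose/exposure of 300 mg BID" envisaged for Phase 2b, and goes on to say that it probably still lies in the efficacious range.

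The surrounding text of 4.3 gives the actual grounds for the dose: earlier experience in healthy participants and allowance for a rise in exposure with hepatic impairment. It cites "repeated doses up to 1800 mg/day (600 mg Q8H; C2541002") as tolerated, states that "the results at the proposed dose of 100 mg in this study can be extrapolated to other doses" because the PK is roughly dose-proportional, and says that "a 3-fold increase likely represents the worst-case estimate for change in plasma exposure in this study" for severe impairment.

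Two other places bear on the point. Section 2.3 says "The data from this study will contribute to dosing recommendations of PF-06865571 for the treatment of NASH" and puts the study dose 15-fold below the highest single dose given so far. Section 4.2 reports that the short half-life "resulted in minimal accumulation upon repeated dosing of both Q8H and Q12H frequency".

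**The concern.** The sentence contradicts itself as written, and no redaction or extraction fault explains it. It is also the only sentence in the available text that relates the tested dose to the planned Phase 2b maximum. A reader who takes one half at face value would think that the hepatic-impairment result has to be carried up 2-fold. On the basis that the sentence names, total daily dose, the step is 6-fold.

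That could matter because the study exists to inform dosing in impaired patients, and the error makes the tested dose look closer to the planned maximum than it is. If the justification for the dose, the extrapolation or a safety margin rested on the fraction, correcting it could weaken the case for the design. The question is whether anything does rest on it.

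**Working it through.** **Inputs**

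- Study dose: 100 mg, single (Protocol 4.3).
- Comparator: 300 mg BID (Protocol 4.3); BID is defined as twice daily (Appendix 9).
- Stated fraction: one half (Protocol 4.3).
- Highest repeated dose: 600 mg Q8H, given as 1800 mg/day (Protocol 4.3).
- Highest single dose: 1500 mg (Protocol 2.3 and 4.3).
- Worst-case exposure increase in this study: 3-fold (Protocol 4.3).

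**Step 1: do the protocol's other dose figures reproduce?**

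- 600 mg × 3 administrations = 1800 mg/day, as stated.
- 1500 / 100 = 15-fold, as stated in 2.3.

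So the section's own convention for a daily dose is dose per administration times administrations per day.

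**Step 2: the stated fraction**

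- Total daily dose: 100 / (300 × 2) = 100 / 600 = 0.167, one-sixth.
- Per administration: 100 / 300 = 0.333, one-third.

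Neither equals 0.5, so the stated fraction does not reproduce.

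**Step 3: size of the discrepancy**

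| Basis | Actual step up | Step implied by one half | Understated by |
|---|---|---|---|
| Total daily dose (daily AUC) | 600 / 100 = 6-fold | 2-fold | 6 / 2 = 3 |
| Per administration (Cmax, given minimal accumulation) | 300 / 100 = 3-fold | 2-fold | 3 / 2 = 1.5 |

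The factor of 3 therefore holds for daily dose only.

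**Step 4: what uses the fraction?**

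- *Primary estimate.* Protocol 9.4.2.3 and SAP 8.2 estimate Test/Reference ratios of geometric means from a one-way ANOVA on log AUC and Cmax. If exposure in cohort g is proportional to dose, AUC_g(D) = k_g × D, then the ratio at dose D is (k_T × D) / (k_R × D) = k_T / k_R. The dose cancels, so a 2-fold and a 6-fold gap give the same carried-over ratio.
- *Range.* Protocol 9.2 describes single doses from 5 mg to 1500 mg. Both 300 mg and 600 mg lie inside it.
- *Sample size and Table 2.* These use between-participant standard deviations of 0.19 (log AUCinf) and 0.17 (log Cmax) with 6 per cohort. No dose fraction enters.
- *Risk in this trial.* The 3-fold worst case at 100 mg is 3 × 100 = 300 mg-equivalent, against 1500 mg already given as a single dose: 1500 / 300 = 5-fold lower. The fraction does not enter here either.
- *Eligibility, sampling times and the SAP.* None refers to the fraction, and the SAP does not repeat the sentence.

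**The case for a change.** The strongest case for acting runs as follows. The sentence is wrong on its face, it sits in the section that investigators and ethics committees read to judge the dose, and it errs in the flattering direction. Apply the 3-fold worst case to 600 mg/day, with dose proportionality and minimal accumulation, and the daily exposure is equivalent to 3 × 600 = 1800 mg/day. That equals the highest repeated dose studied. A reader who relied on one half would not see this.

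The inconsistency stands. The margin argument does not, for four reasons.

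- The protocol confines its worst case to this study, a single 100 mg dose. Moving it to 300 mg BID in severe impairment makes a statement about another trial, and this protocol gives no margin for that setting that would need restating.
- The figure of 1800 mg/day concerns AUC. The Cmax increase predicted for Child-Pugh C is 1.5-fold. The protocol also reports that no maximum tolerated dose was reached, so 1800 mg/day is the top of what was tried and not a known limit.
- The sentence is about whether 100 mg is pharmacologically relevant. For the participants enrolled here, one-sixth of a later maximum is a smaller relative dose than one half, so the slip does not hide a risk to them.
- The sentence cannot be rescued by noting that 3 × 100 = 300 is half of 600. It does not describe the dose in those terms. Equally, the documents do not show whether the fraction, the comparator regimen or the words about total daily dose are at fault, so it would be wrong to assert which one is.

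One limit remains. The protocol describes the earlier experience as coming from healthy adults and, for repeated doses, patients with NAFLD. Proportionality in patients with hepatic impairment is therefore assumed. That assumption is needed for any extrapolation from one dose level, and correcting the fraction would neither strengthen nor weaken it.

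**Conclusion.** The slip is real but clerical. The stated one half should read against 0.167 on total daily dose or 0.333 per administration if the printed 100 mg and 300 mg BID both stand. That is a discrepancy of 3-fold or 1.5-fold according to the basis. The figures in the sentence need to be reconciled with the Phase 2b plan, and the documents alone cannot settle which is in error.

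No change to the plan follows. The fraction is an aside in rationale text. Correcting it leaves the dose, eligibility, sampling, sample size, Table 2, the analysis and the interpretation of the ratios as they are. The quantified margin in Section 2.3 (15-fold) is right and does not depend on it.

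The conclusion rests on the protocol's statement of approximate dose proportionality and on its report of minimal accumulation at Q8H and Q12H. If proportionality failed, extrapolation from 100 mg would be uncertain whatever fraction the sentence gave.

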4.4. End of Study Definition

A participant is considered to have completed the study if he/she has completed all phases of the study including the follow-up visit via telephone contact shown in the [schedule of activities](#).

The end of the study is defined as the date of the follow-up visit via telephone contact, shown in the [schedule of activities](#), for the last participant in the trial globally.

5. STUDY POPULATION

This study can fulfill its objectives only if appropriate participants are enrolled. The following eligibility criteria are designed to select participants for whom participation in the study is considered appropriate. All relevant medical and nonmedical conditions should be taken into consideration when deciding whether a particular participant is suitable for this protocol.

Prospective approval of protocol deviations to recruitment and enrollment criteria, also known as protocol waivers or exemptions, is not permitted.

5.1. Inclusion Criteria

5.1.1. Participants in All Cohorts

Participants are eligible to be included in the study only if all of the following criteria apply:

Age and Sex:

1. Male and female participants between the ages of 18 (or the minimum country-specific age of consent if >18) and 70 years, inclusive, at the Screening visit:
 - Refer to [Appendix 4](#) for reproductive criteria for male ([Section 10.4.1](#)) and female ([Section 10.4.2](#)) participants.

Type of Participant and Disease Characteristics:

2. Participants who are willing and able to comply with all scheduled visits, treatment plan, laboratory tests, lifestyle considerations, and other study procedures.

Weight:

3. Body mass index (BMI) of 17.5 to 35.4 kg/m², inclusive; and a total body weight >50 kg (110 lb), at the Screening visit; with a single repeat assessment of total body weight (and hence BMI), *on a separate day* permitted to assess eligibility, if needed.

Informed Consent:

4. Capable of giving signed informed consent as described in [Appendix 1](#), which includes compliance with the requirements and restrictions listed in the informed consent document (ICD) and in this protocol.

5.1.2. ***Additional*** Inclusion Criteria for Participants without Hepatic Impairment (Cohort 1 ***Only***)

1. At Screening, no clinically relevant abnormalities identified by a detailed medical history, full physical examination, including blood pressure and pulse rate measurement, 12-lead ECG and clinical laboratory tests, as assessed by the sponsor-identified central laboratory.
2. At Screening, participants must meet the demographic-matching criteria, including:
 - A body weight that is ± 10 kg of the average of the pooled hepatic impairment cohorts (Cohorts 2, 3, and 4), as provided by the sponsor;
 - An age that is ± 5 years of the average of the pooled hepatic impairment cohorts (Cohorts 2, 3, and 4), as provided by the sponsor;
 - ***Attempts will be made*** to ensure that the male-to-female distribution in Cohort 1 is comparable to that in the pooled hepatic impairment cohorts (Cohorts 2, 3, and 4).
3. No known or suspected hepatic impairment; including at Screening. Participants meet **all** the following criteria, as assessed by the sponsor-identified central laboratory, with a single repeat permitted to assess eligibility, if needed:
 - Alanine aminotransferase (ALT) \leq upper limit of normal (ULN);
 - Aspartate aminotransferase (AST) \leq ULN;
 - Total bilirubin \leq ULN;

NOTE: Participants with a history of Gilbert syndrome (and hence elevated total bilirubin) are eligible provided direct bilirubin level is \leq ULN **plus** ALT and AST are \leq ULN **plus** alkaline phosphatase, hemoglobin, **and** reticulocyte count are all \leq ULN;

 - Albumin \leq ULN;
 - Prothrombin time \leq ULN.

5.1.3. ***Additional*** Inclusion Criteria for Participants with Impaired Hepatic Function (Cohorts 2, 3, and 4 ***Only***)

1. Stable hepatic impairment that meets the criteria for Class A, B, ***or*** C of the modified Child-Pugh classification (refer to [Appendix 8](#)) with no clinically significant change in disease status within the 28 days prior to the Screening visit, as documented by the participant's recent medical history (*for example*: no worsening clinical signs of hepatic impairment, no worsening of total bilirubin or prothrombin time (PT) by more than 50%).

2. Stable concomitant medications for the management of individual participants' medical history; ***on a case-by-case basis***, with input from the sponsor, participants receiving fluctuating concomitant medication/treatment may be considered if the underlying disease is under control.
3. Participant is willing and able to abide by the lifestyle guidelines described in [Section 5.4](#) of this protocol.

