4. STUDY DESIGN

4.1. Overall Design

This is a Phase 1, non-randomized, open-label, single-dose, parallel-cohort, multicenter study to compare the pharmacokinetics of PF-06865571 in adult participants with varying degrees of hepatic impairment relative to participants without hepatic impairment after a single, oral 100 mg dose administered in the fed state. A total of approximately 24 participants with varying degrees of hepatic function will be dosed in the study as shown in [Table 1](#).

Table 1. Hepatic Function Categories Based on Child Pugh Score

Cohort	Description	Child-Pugh Score	Number of Subjects
1	Without hepatic impairment	Not Applicable	6a
2	Mild hepatic impairment	Class A (5 to 6 points)	6
3	Moderate hepatic impairment	Class B (7 to 9 points)	6
4	Severe hepatic impairment	Class C (10 to 15 points)	6b

[figure not shown]
- a. Additional participants may be dosed to a maximum of 8 participants to ensure mean age ± 5 years and mean body weight ± 10 kg of this cohort is aligned with the pooled average assessed when $\geq 75\%$ of participants are dosed across the other 3 cohorts.
- b. If recruitment across the sites selected proves to be prohibitive, study will dose only 4 participants in this cohort.

Categorization of participants into Cohort 2-4, inclusive, will be done based on Child-Pugh scores determined, as described in [Appendix 8](#), at the Screening visit. Participants will be dosed in a staged manner such that those with moderate and severe hepatic impairment (Cohorts 3 and 4) will be evaluated first. Dosing in participants with mild hepatic impairment (Cohort 2) will initiate when approximately 50% of the total participants in Cohorts 3 and 4 have been dosed. Participants without hepatic impairment (Cohort 1) will be recruited near the end of the study to match the average demographics (at a minimum, age and weight; and gender as much as practically possible) across the pooled Cohorts 2 through 4. **Approval from the sponsor must be obtained before proceeding with recruitment for participants in Cohort 1 or Cohort 2.**

Participants who prematurely discontinue for non-safety related reasons may be replaced, at the discretion of the principal investigator (PI) and sponsor study team.

The overall study design is summarized in [Figure 1](#). For individual participants, the total duration of participation from the Screening visit to the follow-up visit will range from 5 weeks (minimum) to 9 weeks (maximum).

Figure 1. Study Design

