5.2.1. Additional Exclusion Criteria for Participants without Hepatic Impairment (Cohort 1 Only)

Participants presenting with any of the following will not be included in the study:

1. Evidence of chronic liver disease including history of hepatitis, hepatitis B, or hepatitis C or evidence of any of the following, as assessed by sponsor-identified central laboratory, with a single repeat, permitted to assess eligibility, if needed:
 - Hepatitis B virus, defined by presence of hepatitis B surface antigen (HBsAg);

NOTE: while *not* part of the tests assessed in this study, participants with a previously positive hepatitis B surface antibody result due to vaccination are deemed eligible;

- Hepatitis C infection, defined by presence of hepatitis C antibody (HCVAb) ***and*** HCV ribonucleic acid (RNA).
- 2. History of alcohol abuse or binge drinking and/or any other illicit drug use or dependence within 6 months of Screening. Binge drinking is defined as a pattern of 5 (male) and 4 (female) or more alcoholic drinks in about 2 hours. As a general rule, alcohol intake should not exceed 14 units per week (1 unit = 8 ounces [240 mL] beer, 1 ounce [30 mL] of 40% spirit or 3 ounces [90 mL] of wine).
- 3. Screening ***supine*** 12-lead ECG demonstrating Fridericia method-corrected QT (QTcF) interval >450 millisecond (msec) or a QRS interval >120 msec. If QTcF exceeds 450 msec, or QRS exceeds 120 msec, the ECG should be repeated 2 more times and the average of the 3 QTcF or QRS values should be used to determine the participant's eligibility.
- 4. Screening ***seated*** systolic blood pressure (SBP) \geq 140 mm Hg or diastolic blood pressure (DBP) \geq 90 mm Hg, following \geq 5 minutes of seated rest. If SBP is \geq 140 mm Hg or DBP \geq 90 mm Hg, the blood pressure (BP) assessment should be repeated 2 more times and the average of the 3 BP values should be used to determine eligibility.
- 5. Use of ***chronic*** prescription medications within 7 days or 5 half-lives (whichever is longer) prior to Day 1;

NOTE: Use of selected, limited prescription and non-prescription medications is permitted (refer to [Section 6.5](#) for details).

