10.8. Appendix 8: Child-Pugh Classification (CPC) of Liver Dysfunction

Table 10.8-1: Scoring for Child-Pugh Classification

Cohort	CPC	Level of dysfunction	Total Score (tally based on assessment of parameters in Table 10.8-2)
1	Not Applicable	Without hepatic impairment	Not Applicable
2	A	Mild	5-6
3	B	Moderate	7-9
4	C	Severe	≥10

Table 10.8-2: Derivation of Child-Pugh Classification Score

Assessment Parameters	Assigned score for observed findings		
	1 point	2 points	3 points
Encephalopathy grade ^a (refer to Table 10.8-3 below)	0	1 or 2	3 or 4 ^a
Ascites	Absent	Asymptomatic	Requiring intervention
Serum total bilirubin, mg/dL	<2	2 to 3	>3
Serum albumin, g/dL	>3.5	2.8 to 3.5	<2.8
Prothrombin time, sec prolonged ^b	<4	4 to 6	>6

- a. Subjects with a prior history of Grade 3 or Grade 4 encephalopathy who are *currently* receiving an intervention [for example: lactulose or lactitol, alone or in combination with rifaximin, and/or neomycin] to manage encephalopathy-related signs and symptoms should be scored for encephalopathy grading *based on their presentation while on intervention at the Screening visit* and can be included in this study as long as they do **not** have clinically active Grade 3 or Grade 4 encephalopathy.
- b. As assessed relative to PT control (or upper limit of normal), as reported by sponsor-identified central laboratory

Table 10.8-3: Determination of Encephalopathy Grade

Encephalopathy Grade	Definition
0	Normal consciousness, personality, neurological exam
1	Restless, sleep disturbed, irritable/agitated, tremor, impaired handwriting
2	Lethargic, time-disoriented, inappropriate, asterixis, ataxia
3 ^a	Somnolent, stuporous, place-disoriented, hyperactive reflexes, rigidity
4 ^a	Unrousable coma, no personality/behavior, decerebrate

- a. Subjects with clinically active Grade 3 or 4 encephalopathy are excluded.

CPC should be assessed at Screening only to determine the classification of a given participant.

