8. STATISTICAL METHODOLOGY AND STATISTICAL ANALYSES

8.1. Statistical Methods

For all outputs produced, the following ordering will be used:

Without Hepatic Impairment

Mild Hepatic Impairment

Moderate Hepatic Impairment

Severe Hepatic Impairment.

The effect of the hepatic impairment on PK parameters will be assessed by constructing 90% confidence intervals around the estimated difference between each of the Test (impaired groups) and the Reference (normal hepatic function group) using a one-way ANOVA model based on natural log transformed data.

The relationship between PK parameters and hepatic function parameters (eg, serum albumin concentration, or prothrombin time) will be determined by a linear regression model.

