10. APPENDICES

Appendix 1: SAS CODE FOR ANALYSES

An example of the PROC GLM code is provided below:

```
proc glm data=tab.pk;
       class group;
       model 1&var=group/ss3 clparm alpha=0.1;
       Ismeans group;
       estimate 'Mild vs Normal'
                                          group -1 1 0 0;
       estimate 'Moderate vs Normal'
                                          group -1 0 1 0;
       estimate 'Severe vs Normal'
                                          group -1 0 0 1;
       ods output Estimates = est&var;
       ods output FitStatistics = fit&var;
       ods output ModelANOVA = tst&var;
       ods output OverallANOVA = overall&var;
run;
An example of the PROC REG code is provided below:
proc reg data=tab.pk;
       model l&var=&HepaticFunction/clb alpha=0.1;
       ods output ParameterEstimates = param&var;
       ods output FitStatistics = fit&var;
       ods output ANOVA = reg\&var;
run;
```

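### The Cohort 1 albumin criterion sets only an upper limit, so it cannot detect the low albumin that the protocol itself treats as a sign of hepatic impairment

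*Protocol*

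**What the plan says.** Protocol 5.1.2, criterion 3, applies to Cohort 1 only. It opens "No known or suspected hepatic impairment; including at Screening. Participants meet" all of the laboratory limits that follow, as assessed by the central laboratory, with one repeat permitted. ALT, AST, total bilirubin (with an exception for Gilbert syndrome), albumin and prothrombin time must each be at or below ULN. No lower limit for albumin appears in the section.

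Appendix 8, Table 10.8-2, row "Serum albumin, g/dL", runs the other way: above 3.5 scores 1 point, 2.8 to 3.5 scores 2, and below 2.8 scores 3. High albumin carries no penalty. SAP 8.1 also counts albumin among the "hepatic function parameters (eg, serum albumin concentration, or prothrombin time" that it relates to the PK parameters.

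Protocol Section 5 states that prospective approval of deviations from enrollment criteria, "also known as protocol waivers or exemptions, is not permitted".

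Cohort 1 has 6 participants, and Table 1, footnote a, adds: "Additional participants may be dosed to a maximum of 8 participants". It is the Reference in every primary comparison (Protocol 9.4.2.3, SAP 8.2).

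**The concern.** Criterion 3 exists to add objective limits to the general statement that a control has no hepatic impairment. For ALT, AST, bilirubin and prothrombin time, the side that is bounded is the side that signals impairment. For albumin it is the opposite side. The bullet therefore cannot do the job the list is there for, and it can turn away a candidate for a finding that the protocol nowhere links to impairment.

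What is at stake is the denominator of each Test/Reference ratio. An impaired participant among the controls would be expected to raise Reference exposure. All three ratios for a parameter would then fall, and the effect of hepatic impairment would be understated. With only 6 to 8 controls, one participant carries noticeable weight in the geometric mean.

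**Working it through.** **Step 1. Direction of each bound.** The table compares criterion 3 with Table 10.8-2 for the tests that appear in both.

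| Test | Cohort 1 limit | Side that scores more points |
|---|---|---|
| Total bilirubin | at or below ULN | high |
| Prothrombin time | at or below ULN | prolonged |
| Albumin | at or below ULN | low |

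Only albumin is bounded on the side that earns no extra points.

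**Step 2. The rule applied to values.** The documents do not give the laboratory's ULN, so I assumed 4.8, 5.0 and 5.5 g/dL. The result is the same for all three.

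| Albumin (g/dL) | Meets the bullet? | Albumin points |
|---|---|---|
| 2.5 | yes | 3 |
| 3.0 | yes | 2 |
| 3.5 | yes | 2 |
| 4.2 | yes | 1 |
| ULN + 0.1 | no | 1 |

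The points serve only to show which direction the protocol regards as informative. The protocol does not score Cohort 1.

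**Step 3. The plan's own precision.** Protocol 9.2 gives between-participant SDs on the log scale of 0.19 (AUCinf) and 0.17 (Cmax), with 6 per cohort. Table 2 is reproduced by

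half-width = t(0.95, 20) × SD × √(2/6) × √(χ²(0.80, 20)/20), with t = 1.7247 and χ² = 25.038.

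- AUCinf: 1.7247 × 0.19 × 0.5774 × 1.1189 = 0.2117, so at ratio 1 the interval is 0.81 to 1.24, as in Table 2.
- Cmax: 1.7247 × 0.17 × 0.5774 × 1.1189 = 0.1894, so 0.83 to 1.21, as in Table 2.

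The albumin rule does not enter this calculation.

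**Step 4. Hypothetical shift.** Suppose one of n controls had exposure f times that of the others. The Reference geometric mean is multiplied by f^(1/n), and each ratio by f^(−1/n). Protocol 4.3 supplies f from simulation. For AUCinf, "increases of 1.4-, 2.1-, and 2.9-fold, respectively, are also predicted" for Child-Pugh A, B and C. For Cmax the figures are 1.2, 1.3 and 1.5. I used A and B.

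| Parameter | f | n = 6: ratio × | Change | n = 8: ratio × | Change |
|---|---|---|---|---|---|
| AUCinf | 1.4 | 0.9455 | −5.5% | 0.9588 | −4.1% |
| AUCinf | 2.1 | 0.8837 | −11.6% | 0.9114 | −8.9% |
| Cmax | 1.2 | 0.9701 | −3.0% | 0.9775 | −2.2% |
| Cmax | 1.3 | 0.9572 | −4.3% | 0.9677 | −3.2% |

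At ratio 1 the planned lower limits lie 19% (AUCinf) and 17% (Cmax) below the estimate. With 8 controls and 6 in the Test cohort (22 degrees of freedom), the same formula gives lower limits of 0.82 and 0.84, or 18% and 16% below. Every shift in the table is smaller.

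This comparison is for one such participant. Two of six at 2.1-fold would multiply the AUCinf ratio by 2.1^(−2/6) = 0.781, a fall of 21.9%, which exceeds 19%. That case needs the other safeguards to fail twice.

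**The case against.** The strongest reply is that the albumin bullet does not stand alone. The opening of criterion 3 separately requires no known or suspected hepatic impairment. Criterion 1 of 5.1.2 requires no clinically relevant abnormality on clinical laboratory tests, and albumin is in that panel (Appendix 2). Exclusion 3 of 5.2 and exclusion 6 of 5.2.1 cover laboratory abnormalities at the investigator's judgement. Exclusion 1 of 5.2.1 begins "Evidence of chronic liver disease including history of hepatitis, hepatitis B, or hepatitis C". The other laboratory limits must also be met, and the sponsor must approve both recruitment (4.1) and dosing (5.3) of Cohort 1. Together these would probably keep out most impaired candidates.

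That stands, and it sets the size of the point. It does not rescue the bullet. The provisions that would catch an isolated low albumin rest largely on judgement, and none of them can admit a candidate who fails the upper limit.

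Three stronger readings are tempting, and the documents do not support them:

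- A reader might infer that the criterion lets a Child-Pugh B patient in as a control, since albumin of 2.5 g/dL with every other item at 1 point totals 7. Child-Pugh is marked not applicable to Cohort 1, and passing one bullet is not passing eligibility.
- A reader might infer that needless screen failures will occur. The documents do not say how often albumin exceeds ULN, or that a high value is harmless. They show only that Table 10.8-2 attaches no penalty to it. Such failures are possible, not certain.
- A reader might take the shifts in the working as expected bias. They assign simulated Child-Pugh A or B exposure to someone whose other liver tests are normal, and neither document says that isolated low albumin raises exposure.

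A program's misreading of the PDF is an unlikely explanation. A lower-limit rule would need both a different operator and a different abbreviation, and the abbreviation list defines ULN but no lower limit of normal.

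**Conclusion.** The albumin bullet is wrong as written: it bounds the side that Table 10.8-2 treats as uninformative and leaves the informative side open. This follows from the text alone and does not depend on the ULN.

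The consequence is minor. A low-albumin candidate would have to be stopped by the remaining, largely judgement-based criteria, so the risk to the Reference cohort is low but avoidable. No planned sample size, interval or analysis method changes. The effect on the ratios is hypothetical. With one affected control it is at most 11.6% for AUCinf and 4.3% for Cmax, inside the planned 90% interval half-widths. Those figures assume that this control's exposure equals the simulated Child-Pugh A or B value and that the other controls are unaffected.

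**What to change.** Before Cohort 1 is recruited, amend the albumin bullet in Protocol 5.1.2, criterion 3, so that it agrees in direction with Table 10.8-2: bound albumin on the low side instead of the high side. The documents give no lower limit for controls, so the sponsor should set the threshold.

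The cost is a short amendment with IRB/EC approval (Protocol 10.1.1) and possibly a few more Cohort 1 screen failures for low albumin. Failures for high albumin would no longer arise. Albumin is already in the central-laboratory chemistry panel, so no new test is needed. Cohort 1 is recruited near the end of the study and only after sponsor approval (Protocol 4.1), which leaves time for the change.
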